- ^m Complete and abbreviated PEs are described in [Section 11.7.3](#). Symptom-targeted PEs will occur at any time during the study if triggered by AEs or if deemed necessary by the investigator or healthcare provider.
- ⁿ The ophthalmological examination can be performed at any time during the Screening Period through the Day 1 Visit (before the first dose of study drug). The screening ophthalmological examination does not have to be performed if there is documentation of an examination that met protocol criteria and was within 3 months before the date of informed consent, or if there is documentation of bilateral lens removal for the subject.
- ^o All standard 12-lead ECGs will be performed after the subject has been seated for at least 5 minutes. On Days 1 and 15, ECGs will be collected before dosing and 4 hours (± 1 hour) after dosing. At all other visits, ECGs will be collected before dosing (as applicable). ECGs collected on Day 1 before dosing will be performed in triplicate.
- ^p Sweat chloride will be measured in all subjects. If the value cannot be determined from the screening test, a sweat chloride value documented in the subject's medical record may be used to establish eligibility.
- ^q Spirometry may be performed pre- or post-bronchodilator at the Screening Visit. Spirometry will be performed pre-bronchodilator, before the morning dose of study drugs, and should be performed at approximately the same time at every other study visit. On Days 1 and 15, spirometry will also be performed pre-bronchodilator, 5 hours (± 1 hour) after study drug administration.
- ^r *CFTR* genotyping will be performed for all subjects. If the screening *CFTR* genotype result is not received before Day -28, a previous *CFTR* genotype laboratory report may be used to establish eligibility.

Table 3-3 Study VX15-440-101: Schedule of Assessments for Part 2

Event/Assessment ^a	Screening	Run-in Period		Treatment Period ^b			Washout Period		ETT Visit ^c	Safety Follow-up 28 (± 7) Days After Last Dose ^d
	Days -56 to -29 ^e	Day -28 (± 1 day)	Day -14 ^f (± 1 day)	Day 1	Day 15 (± 2 days)	Day 29 (± 2 days)	Day 43 (± 3 days)	Day 57 (± 3 days)		
G6PD activity test ^t	X									
Serum chemistry and hematology [†]	X	X		X	X	X	X	X	X	X
Coagulation [†]	X	X		X	X	X				X
PK sampling ^v				X	X	X	X		X	
TEZ/IVA dosing ^w		Day -28 through Day 57								
VX-440 or placebo dosing ^x				Day 1 through Day 29						
AEs, medications ^y , treatments and procedures	Continuous from signing of the ICF through the Safety Follow-up Visit									

^s FSH will be measured for any suspected postmenopausal female subjects with at least 12 months of continuous spontaneous amenorrhea.

^t A single blood sample will be collected for the G6PD activity test

^v Blood samples will be collected for PK analysis of VX-440, TEZ, M1-TEZ, IVA, and M1-IVA. On Day 1, samples will be collected before dosing (0 hours) and at 1, 2, 4, and 6 hours after dosing (relative to morning dose). On Day 15, samples will be collected before dosing (0 hours) and at 1, 2, 4, 6, and 8 hours after dosing. On Day 29, a predose sample will be collected before the morning dose of study drug. At the Day 43 Visit, a single blood sample for PK analysis will be collected before the morning dose of TEZ/IVA. At the ETT Visit, a single blood sample for PK analysis will be collected.

^w The last dose of TEZ/ivacaftor will be the morning dose on Day 57.

^x The last dose of VX-440 or placebo will be the morning dose on Day 29.

^y Refer to [Section 9.4](#) for details.

FEV ₁	forced expiratory volume in 1 second
FSH	follicle-stimulating hormone
G6PD	glucose-6-phosphate dehydrogenase
GCP	Good Clinical Practice
GPS	Global Patient Safety
HBE	human bronchial epithelial
HMA	Heads of Medicines Agencies
ICF	informed consent form
ICH	International Conference on Harmonization
IDMC	independent data monitoring committee
IEC	independent ethics committee
█	█
█	█
INN	international nonproprietary name
IPD	important protocol deviation
IRB	institutional review board
IVA	ivacaftor
IWRS	interactive web response system
LFT	liver function test
LUM	lumacaftor
max	maximum value

Abbreviation	Term
MBW	multiple-breath washout
MCP	multiple comparisons procedure
MF	minimum function
min	minimum value
MMRM	mixed-effects model for repeated measures
N	total sample size (e.g., number of subjects treated)
NA	not applicable
OATP1B1	organic anion transporting polypeptide 1B1
OATP1B3	organic anion transporting polypeptide 1B3
P	probability
PD	pharmacodynamic, pharmacodynamics
PE	physical examination
PK	pharmacokinetic, pharmacokinetics
ppFEV ₁	percent predicted forced expiratory volume in 1 second
q12h	every 12 hours
qd	daily
QTc	QT interval corrected
QTcF	QT interval corrected by Fridericia's formula
SAE	serious adverse event
SAP	statistical analysis plan
SD	standard deviation
SE	standard error
TBD	to be determined
TC	triple combination
TE	treatment-emergent
TEAE	treatment-emergent adverse event
TEZ	tezacaftor
ULN	upper limit of normal
USAN	United States adopted name
Vertex	Vertex Pharmaceuticals Incorporated
█	█

5 INTRODUCTION

5.1 Background

Cystic fibrosis (CF) affects more than 70,000 children and adults worldwide¹ and is the most common fatal genetic disease in persons of European descent.² Based on its prevalence, CF qualifies as an orphan disease.^{3,4} CF is caused by a defect in the gene encoding the CF transmembrane conductance regulator (CFTR), an ion channel that regulates the flow of chloride and other ions in epithelia of various tissues, including lungs, pancreas and other gastrointestinal organs, and sweat glands.² Decreased CFTR activity in people with CF results in multisystem pathology⁵, beginning at birth. Despite progress in the treatment of CF with antibiotics and mucolytics, the median predicted survival age for a person with CF is approximately 40 years.^{2, 6} More effective treatments are needed for CF.

To address this medical need, Vertex Pharmaceuticals Incorporated is developing treatment regimens that include CFTR modulators to target the underlying cause of CF: the defective CFTR protein. Two types of CFTR modulators have been developed: potentiators, which increase the channel gating activity of the CFTR protein, and correctors, which increase the quantity of CFTR at the cell surface. Because potentiators can increase the activity of CFTR protein delivered to the cell surface by correctors, CFTR potentiators and correctors are complementary therapeutic approaches.

Ivacaftor (IVA; Kalydeco[®]), the first CFTR modulator developed by Vertex, is an orally administered CFTR potentiator that increases the channel-open probability of CFTR protein to enhance chloride transport. Globally, Kalydeco is indicated for the treatment of CF in patients as young as 2 years who have the *G551D* and certain other gating mutations, as well as the *R117H* mutation in the *CFTR* gene in certain regions.⁷

Lumacaftor (LUM; VX-809) and tezacaftor (TEZ; VX-661) are orally administered first-generation CFTR correctors developed by Vertex that act directly on CFTR to improve its cellular processing and trafficking, thereby increasing the quantity of functional F508del-CFTR protein at the cell surface. *F508del*, the most prevalent mutation in people with CF, occurs in about 83% of CF patients of European descent, and results in a decreased quantity of CFTR protein at the cell surface. Orkambi[™] (LUM/IVA combination therapy) is approved in the US, EU, Canada, and Australia for patients 12 years and older who are homozygous for *F508del*. Phase 3 studies of TEZ/IVA combination therapy are ongoing in populations that are homozygous or heterozygous for *F508del*.

VX-440 is a second-generation CFTR corrector that acts through a different site of the CFTR protein than LUM and TEZ. In vitro, VX-440 improves the processing and trafficking of F508del-CFTR, thereby increasing the quantity of functional F508del-CFTR protein at the cell surface. VX-440 has been studied in vitro in combination with the first generation corrector TEZ. Consistent with different mechanisms of action, the effects of VX-440 and TEZ are additive. The activity of the CFTR protein delivered to the cell surface by VX-440, alone or in combination with TEZ, is potentiated by IVA. In human bronchial epithelial (HBE) cells derived from CF patients homozygous for *F508del*, the triple combination (TC) of VX-440, TEZ, and IVA increased CFTR-mediated chloride transport more than the dual combinations (VX-440 and TEZ; VX-440 and IVA; TEZ and IVA) or individual agents (VX-440; TEZ; IVA). These data, as

well as the nonclinical pharmacokinetic (PK) and safety profile, support the development of VX-440 in combination with other CFTR modulators for the treatment of CF.

5.2 Rationale for the Present Study

The present study is the first clinical study of VX-440 in subjects with CF and is designed to evaluate the safety and efficacy of VX-440 in [REDACTED] triple combination with TEZ and IVA.

VX-440 has been studied in vitro and in vivo, and the safety profile in the nonclinical toxicology studies supports continued development of VX-440 with appropriate measures given the potential for teratogenicity.^{8,9}

The safety, tolerability, and PK of VX-440 as monotherapy or in TC with TEZ/IVA are being evaluated in healthy subjects (Study VX15-440-001 [Study 001] and VX16-440-002 [Study 002]). Single doses of VX-440 up to 1600 mg and multiple doses of VX-440 up to 600 mg q12h have been generally safe and well tolerated. Multiple doses of VX-440 up to 600 mg q12h in TC with TEZ (100 mg qd) and IVA (up to 300 mg q12h) were also safe and well tolerated.

Based on the data from nonclinical and clinical studies of VX-440, TEZ, and IVA to date and the current unmet medical need for new treatments for CF, there is potential for benefit to CF patients from the development of this treatment. Therefore, the overall risk-benefit balance for this study is considered to be acceptable.

6 STUDY OBJECTIVES

6.1 Primary Objectives

- To evaluate the safety and tolerability of VX-440 in [REDACTED] triple combination with TEZ and IVA
- To evaluate the efficacy of VX-440 in [REDACTED] triple combination with TEZ and IVA

6.2 Secondary Objectives

- To evaluate the pharmacodynamic (PD) effect of VX-440 in [REDACTED] triple combination with TEZ and IVA on sweat chloride concentrations
- To evaluate the PK of VX-440 when administered in [REDACTED] triple combination with TEZ and IVA
- To evaluate the PK of TEZ, IVA, and their respective metabolites when administered with VX-440

7 STUDY ENDPOINTS

7.1 Primary Endpoints

- Safety and tolerability assessments based on adverse events (AEs), clinical laboratory values, standard 12-lead electrocardiograms (ECGs), vital signs, and pulse oximetry
- Absolute change in percent predicted forced expiratory volume in 1 second (ppFEV₁) from baseline through Day 29 (Parts 1 and 2) [REDACTED]

7.2 Secondary Endpoints

- Absolute change in sweat chloride concentrations from baseline through Day 29 (Parts 1 and 2) [REDACTED]
- Relative change in ppFEV₁ from baseline through Day 29 (Parts 1 and 2) [REDACTED]
- [REDACTED]
- [REDACTED]
- [REDACTED]
- [REDACTED]
- [REDACTED]
- [REDACTED]
- [REDACTED]
- PK parameters of VX-440, TEZ, M1-TEZ, IVA, and M1-IVA

[REDACTED]

8 STUDY DESIGN

8.1 Overview of Study Design

This is a Phase 2, randomized, double-blind, placebo- and TEZ/IVA-controlled, parallel-group, multicenter study designed to evaluate the safety and efficacy of VX-440 in [REDACTED] triple combination with TEZ and IVA.

Approximately 198 subjects with CF will be enrolled across Parts 1 [REDACTED]. Enrollment of Parts 1 [REDACTED] will be sequential, while enrollment of Part 2 will be in parallel with Part 1 Cohort 1B. [REDACTED]

Part 1 will consist of 2 cohorts: Cohort 1A and Cohort 1B. The start of dosing of Cohort 1A and Cohort 1B will be sequential. After all Cohort 1A subjects complete the Day 15 Visit, a blinded review of all available safety and PK data will be conducted by the Vertex study team and lead investigator(s). Dosing of Cohort 1B will begin after the blinded review, if supported by safety and PK data.

Part 2 will initiate after the Cohort 1A blinded review, if supported by safety and PK data.

[REDACTED]

Key study elements of each part are summarized in Table 8-1. The treatment arms and randomization ratios for each part are summarized in Table 8-2. A schematic of the study design is shown in Figure 8-1 (Parts 1 and 2) [REDACTED]

Interim analyses are described in Section 12.3.6.1.

All parts of this study will include a Screening Period, Treatment Period, and Safety Follow-up Visit. Part 2 will also include a 4-week Run-in Period and a 4-week Washout Period after the Treatment Period.

Table 8-1 Key Study Elements by Part

	Part 1 ^a	Part 2
Genotype	F508del/MF	F508del/F508del
Age	≥18 years	≥18 years
ppFEV ₁ criteria	≥40 to ≤90	≥40 to ≤90
Number of subjects	Approximately 42 ^a	Approximately 24
Stratification ^c	ppFEV ₁ ^d • ≥70 • <70	ppFEV ₁ • ≥70 • <70
Study design	Parallel	Parallel
Comparator	Placebo	TEZ/IVA
VX-440 treatment duration	4 weeks	4 weeks

IVA: ivacaftor; MF: minimal function; ppFEV₁: percent predicted forced expiratory volume in 1 second; q12h: every 12 hours; TC: triple combination; TEZ: tezacaftor

[figure not shown]
^a Part 1 consists of Cohort 1A and Cohort 1B. Approximately 10 subjects will be in Cohort 1A and approximately 32 subjects will be in Cohort 1B [REDACTED]

^c Additional stratification information is provided in Section 8.1.3.

^d Stratification will be conducted for Cohort 1B subjects only.

Table 8-2 Treatment Arms and Planned Doses by Part

Part	Treatment Arm	VX-440 Dosage	TEZ Dosage	IVA Dosage
Part 1 Cohort 1A 4:1	TC-1A Triple placebo	200 mg q12h Placebo	100 mg qd Placebo	150 mg q12h Placebo
Part 1 Cohort 1B 2:1:1	TC-1B-high TC-1B-low Triple placebo	600 mg q12h ^a 200 mg q12h Placebo	50 mg q12h 50 mg q12h Placebo	300 mg q12h ^a 150 mg q12h Placebo
Part 2^b 3:1	TC-2 TEZ/IVA	600 mg q12h ^a Placebo	50 mg q12h 100 mg qd	300 mg q12h ^a 150 mg q12h

In the “TC-1B-high” and “TC-2” treatment arms, the dosage of VX-440 will be determined based on safety and PK data from Cohort 1A. The planned dose is shown, but may be reduced to 400 mg q12h.

^b In Part 2, all subjects will also receive TEZ 100 mg qd/IVA 150 mg q12h during the Run-in Period and the Washout Period.

[figure not shown]
[figure not shown]
[figure not shown]

Figure 8-1 Schematic of the Study Design for Parts 1 and 2

[figure not shown]
Part 1 Cohort 1A: *F508del*/MF (N ~ 10)
Randomization: 4:1

[figure not shown]
Part 1 Cohort 1B: *F508del*/MF (N ~ 32)
Randomization: 2:1:1
Stratification: ppFEV₁: ≥70 versus <70

Part 2: *F508del*/*F508del* (N ~ 24)
Randomization: 3:1
Stratification: ppFEV₁: ≥70 versus <70

IVA: ivacaftor; MF: minimal function; N: number of subjects; ppFEV₁: percent predicted forced expiratory volume in 1 second; q12h: every 12 hours; qd: daily; TEZ: tezacaftor; TC: triple combination
Notes: Schematic is not drawn to scale. TC includes VX-440, TEZ, and IVA. The dose of each component of the TC is shown by treatment arm in Table 8-2. In Part 2, the dose of TEZ/IVA during the Run-in Period and the Washout Period will be TEZ 100 mg qd/IVA 150 mg q12h. Additional stratification information is provided in Section 8.1.3.

Study visits and assessments to be conducted are shown in [Table 3-1](#) (Part 1 Cohort 1A), [Table 3-2](#) (Part 1 Cohort 1B), [Table 3-3](#) (Part 2), [REDACTED]

8.1.1 Screening

For Parts 1 [REDACTED] the Screening Period will occur within 28 days before the first dose of study drug in the Treatment Period. For Part 2, the Screening Period will occur within 28 days before the first dose of TEZ/IVA in the Run-in Period.

Assessments to be conducted will be used to confirm that subjects meet the eligibility criteria for the study. The investigator (or an appropriate authorized designee) will obtain informed consent and assent, if applicable, from each subject before any study procedure takes place.

The screening ophthalmologic examination does not have to be performed if there is documentation of an examination that met protocol criteria and was within 3 months before the date of informed consent (or assent, when applicable; [Section 11.7.6](#)) or if there is documentation of bilateral lens removal for the subject.

8.1.1.1 Repetition of Screening Assessment(s)

Repetition of individual screening assessment(s) that did not meet eligibility criteria is not permitted with the following exceptions:

- If there is clear evidence of a laboratory error (e.g., hemolyzed sample) or equipment malfunction, collection of a repeat sample for the appropriate laboratory test or assessment may be permitted with the approval of the medical monitor.
- Exclusionary liver function test (LFT) levels, which may be retested once within 14 days of the original screening date, with approval of the medical monitor.

If screening spirometry measurements fail to meet acceptability and repeatability criteria as specified by American Thoracic Society/European Respiratory Society guidelines¹⁰, repeat spirometry evaluation may be performed once.

If repeat values of the individual assessment(s) are within the eligibility criteria and completed within the screening window, then the subject is eligible for the study.

8.1.1.2 Rescreening

Subjects may only be rescreened with the approval of the medical monitor. If a subject is rescreened, all screening assessments will be repeated except for *CFTR* genotyping, follicle-stimulating hormone (FSH) level (if serum FSH level was ≥ 40 mIU/mL during prior screening), G6PD activity test (if total bilirubin level was $< 2 \times$ upper limit of normal [ULN] during prior screening), sweat chloride level, and the ophthalmologic examination (if documentation shows it was performed within the last 3 months). If a subject is rescreened, the new screening window will begin once the first rescreening assessment has been initiated.

8.1.1.3 Extension of Screening Period Window

A subject may have the Screening Period window extended by 2 weeks, without medical monitor approval, for the following reasons:

- Repetition of the Screening Period assessments (Section 8.1.1.1)
- Unexpected operational or logistic delays, or to meet the eligibility criteria
- Scheduling of ophthalmologic examination (Section 11.7.6)
- Repetition of spirometry assessment if results are of poor quality

A subject may have the Screening Period window extended by 4 weeks, without medical monitor approval, for the following reason:

- For Parts 1 [REDACTED] subjects, washout of TEZ/IVA during the Screening Period if enrolling from Study VX14-661-110 (Study 661-110)

8.1.2 Run-in Period (Part 2)

The Run-in Period will have a total duration of 4 weeks and is designed to establish a reliable on-treatment (TEZ/IVA) baseline for the Treatment Period. Subjects will receive TEZ 100 mg qd/IVA 150 mg q12h during the Run-in Period. The first dose of TEZ/IVA will be administered at the Day -28 Visit. The last dose of TEZ/IVA within the Run-in Period will be administered on Day -1 (1 day before the Day 1 Visit).

8.1.3 Treatment Period

The Treatment Period will last approximately 4 weeks for Parts 1 and 2, [REDACTED]. Study drug administration details are provided in [Section 10.2](#).

For all parts, subjects must meet both of the following criteria to continue into the Treatment Period:

- Must have stable CF disease (as judged by the investigator) and have remained on a stable CF medication regimen during the 28 days before the Day 1 Visit. (For example, subjects cannot have an acute upper or lower respiratory infection, pulmonary exacerbation, or changes in therapy [including antibiotics] for pulmonary disease within 28 days before the Day 1 Visit.)
- Must not have had an acute non-CF illness (e.g., gastroenteritis) within the 14 days before the Day 1 Visit.

If these criteria are not met, subjects may not be randomized and enter into the Treatment Period.

Randomization will occur before the first dose of study drug during the Treatment Period and may occur on Day 1 or Day -1 after all inclusion and exclusion criteria and the criteria for entry into the Treatment Period have been confirmed. Randomization will be stratified according to the criteria shown in [Table 8-1](#). For ppFEV₁ stratification, Day -14 values will be used for subjects in Part 2 who are naïve to TEZ/IVA treatment, while screening ppFEV₁ values will be used for all other subjects, including subjects in Parts 1 [REDACTED].

For Part 2, subjects who prematurely discontinue TEZ/IVA during the Run-in Period will not be randomized or participate in the Treatment Period.

[REDACTED]

8.1.4 Washout Period (Part 2)

The Washout Period will last approximately 4 weeks and is designed to allow for the measurement of VX-440 off-treatment effects. Subjects will receive TEZ 100 mg qd/ IVA 150 mg q12h during the Washout Period.

8.1.5 Follow-up

There will be an outpatient Safety Follow-up Visit occurring approximately 28 days after the last dose of study drug for subjects who complete study drug dosing and for subjects who prematurely discontinue study drug dosing.

The following Part 2 subjects will not have a Safety Follow-up Visit:

- Part 2 subjects who do not meet the criteria to enter the Treatment Period (Section 8.1.3), and re-enter Study 661-110
- Part 2 subjects who complete the Day 57 Visit and re-enter Study 661-110

All other Part 2 subjects will have a Safety Follow-up Visit.

8.1.6 Early Termination of Treatment

If a subject prematurely discontinues treatment, an Early Termination of Treatment (ETT) Visit should be scheduled as soon as possible after the decision to terminate study drug treatment. Subjects who prematurely discontinue treatment will also be required to complete the Safety Follow-up Visit, approximately 28 days after their last dose of study drug.

If the ETT Visit occurs 3 weeks or later following the last dose of study drug, then the ETT Visit will replace the Safety Follow-up Visit, and a separate Safety Follow-up Visit will not be required.

If a subject withdraws from the study and also withdraws consent for disclosure of future information, no further evaluations should be performed and no additional data should be collected. Vertex may retain and continue to use any data collected before such withdrawal of consent.

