3 SCHEDULE OF ASSESSMENTS

The schedule of assessments from the Screening Period through the Safety Follow-up Visit are provided in [Table 3-1](#) for Part 1 Cohort 1A, [Table 3-2](#) for Part 1 Cohort 1B, [Table 3-3](#) for Part 2, [REDACTED]

All visits will be scheduled relative to the Day 1 Visit (first dose of VX-440 or VX-440 matched placebo).

The CFQ-R assessment must be completed before any other assessment at the clinic visits when it is required. For remaining assessments, assessments may be performed in any order when more than 1 assessment is required at a particular time point. (See [Section 11.1.](#))

Table 3-1 Study VX15-440-101: Schedule of Assessments for Part 1 (Cohort 1A)

Event/Assessment ^a	Screening	Treatment Period ^b				Day 43 (± 3 days)	ETT Visit ^c	Safety Follow-up 28 (± 7) Days After Last Dose
	Days -28 to -1 ^d	Day 1	Day 8 (± 1 day)	Day 15 (± 2 days)	Day 29 (± 2 days)			
Informed consent	X							
Randomization ^e		X						
Demographics	X							
Medical history	X							
Ophthalmological history	X							
CFQ-R ^{f,g}		X		X	X	X	X ^h	X
Weight ⁱ	X	X	X	X	X	X	X	X
Height ⁱ	X							
Vital signs ^j	X	X	X	X	X	X	X	X
Pulse oximetry ^j	X	X	X	X	X	X	X	X

^a All assessments will be performed before dosing, unless noted otherwise. Assessments that are collected before and after dosing will only be collected once if study drug is not administered on the day of the visit (i.e., if subject prematurely discontinued study drug treatment).

^b To be eligible to continue into the Treatment Period, subjects must have stable CF disease and have remained on stable CF medication regimen during the 28 days before the Day 1 Visit AND must not have had an acute non-CF illness within 14 days before the Day 1 Visit. See [Section 8.1.3](#).

^c If the subject prematurely discontinues study treatment, an ETT Visit should be scheduled as soon as possible after the decision to terminate study drug treatment. Subjects who prematurely discontinue treatment will also be required to complete the Safety Follow-up Visit. If the ETT Visit occurs 3 weeks or later following the last dose of study drug, then the ETT Visit will replace the Safety Follow-up Visit, and a separate Safety Follow-up Visit will not be required.

^d All screening results must be reviewed by an appropriately qualified member of the investigator's team before randomization, unless noted otherwise.

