ⁿ Sweat chloride will be measured in all subjects. If the value cannot be determined from the screening test, a sweat chloride value documented in the subject's medical record may be used to establish eligibility.

^o Spirometry may be performed pre- or post-bronchodilator at the Screening Visit. Spirometry will be performed pre-bronchodilator, before the morning dose of study drugs, and should be performed at approximately the same time at every other study visit. On Days 1 and 15, spirometry will also be performed pre-bronchodilator 5 hours (± 1 hour) after study drug administration.

^p *CFTR* genotyping will be performed for all subjects. If the screening *CFTR* genotype result is not received before randomization, a previous *CFTR* genotype laboratory report may be used to establish eligibility.

^q FSH will be measured for any suspected postmenopausal female subjects with at least 12 months of continuous spontaneous amenorrhea.

Table 3-1 Study VX15-440-101: Schedule of Assessments for Part 1 (Cohort 1A)

Event/Assessment ^a	Screening	Treatment Period ^b				Day 43 (± 3 days)	ETT Visit ^c	Safety Follow-up 28 (± 7) Days After Last Dose
	Days -28 to -1 ^d	Day 1	Day 8 (± 1 day)	Day 15 (± 2 days)	Day 29 (± 2 days)			
G6PD activity test ^f	X							
Serum chemistry and hematology ^g	X	X	X	X	X	X	X	X
Coagulation ^g	X	X		X	X			X
PK sampling ^h		X	X	X	X	X	X	
Study drug dosing ^u		Day 1 through Day 29						
AEs, medications ^v , treatments, and procedures	Continuous from signing of the ICF through the Safety Follow-up Visit							

r

Blood samples will be collected for PK analysis of VX-440, TEZ, M1-TEZ, IVA, and M1-IVA. On Day 1, samples will be collected before dosing (0 hours) and at 1, 2, 4, and 6 hours after dosing (relative to the morning dose). On Days 8 and 29, a predose sample will be collected before the morning dose of study drug. On Day 15, samples will be collected before dosing (0 hours) and at 1, 2, 4, 6, and 8 hours after dosing. At the Day 43 and the ETT Visits, a single blood sample for PK analysis will be collected.

^u The last dose of study drug will be the morning dose on Day 29.

^v Refer to [Section 9.4](#) for details.

Table 3-2 Study VX15-440-101: Schedule of Assessments for Part 1 (Cohort 1B)

Event/Assessment ^a	Screening	Treatment Period ^b			Day 43 (± 3 days)	ETT Visit ^c	Safety Follow-up 28 (± 7) Days After Last Dose
	Days -28 to -1 ^d	Day 1	Day 15 (± 2 day)	Day 29 (± 2 day)			
Informed consent	X						
Randomization ^e		X					

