12.3.5 Safety Analysis

A coprimary objective of the study is the evaluation of safety and tolerability. All safety analyses will be based on data from the TE Period for all subjects in the Safety Set.

The overall safety profile of study drug will be assessed based on the following safety and tolerability endpoints:

- Treatment-emergent adverse events (TEAEs)
- Clinical laboratory values (i.e., hematology, serum chemistry, coagulation, and urinalysis)
- ECGs
- Vital signs
- Pulse oximetry

All safety data will be summarized by treatment group and overall, for each Part.

All safety data will be presented in individual subject data listings.

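### An Early Termination Visit that replaces Safety Follow-up drops the coagulation test and complete examination scheduled at the visit it replaces

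*Protocol*

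**What the plan says.** Protocol Section 8.1.6 sets the rule for an ETT Visit held at least 3 weeks after dosing has stopped: "then the ETT Visit will replace the Safety Follow-up Visit". The subject then needs no further follow-up visit. Footnote c of Tables 3-1 (Cohort 1A), 3-2 (Cohort 1B) and 3-3 (Part 2) repeats the rule. The last column of each table is headed "Safety Follow-up 28 (± 7) Days After Last Dose".

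In each table the coagulation row is marked at Safety Follow-up and blank at ETT. The physical examination row reads complete at Safety Follow-up and abbreviated at ETT. SAP Appendix A (Tables 11-1 to 11-3) carries the same entries.

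Protocol Section 7.1 places clinical laboratory values among the primary safety endpoints, and Section 12.3.5 spells out what they contain: "Clinical laboratory values (i.e., hematology, serum chemistry, coagulation, and urinalysis". SAP Section 8.1 expressly allows for subjects who have no Safety Follow-up because a late ETT Visit replaced it.

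**The concern.** One visit is allowed to stand in for another that collects more. For a subject on this route the replacing ETT Visit is the last scheduled contact, so no later visit recovers what it omits. What is lost is a post-treatment result on a component of a primary safety endpoint, in a subject who stopped treatment early, in the first study of VX-440 in people with CF. Early stoppers are the subjects whose safety data matter most for judging tolerability.

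The omission looks unintended. Chemistry and hematology, urinalysis, ECG, vital signs, pulse oximetry and a serum pregnancy test are scheduled at both visits. Among the safety assessments, only coagulation and the extent of the examination differ.

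**Working it through.** The plan gives no figure on this point, so the check sets the tables beside the replacement rule and then enumerates the stopping days.

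**Step 1: content of the two visits** (Protocol Tables 3-1 to 3-3; examination content from Section 11.7.3)

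| Assessment | ETT | Safety Follow-up |
|---|---|---|
| Chemistry, hematology, urinalysis | yes | yes |
| ECG, vital signs, oximetry | yes | yes |
| Pregnancy test | serum | serum |
| Coagulation | none | yes |
| Physical examination | abbreviated (5 systems) | complete (9 systems) |

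The abbreviated examination leaves out head/neck/thyroid, lymph nodes, musculoskeletal and neurological: 9 − 5 = 4 systems.

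**Step 2: timing.** The Safety Follow-up window is 28 − 7 = 21 to 28 + 7 = 35 days after the last dose. The replacement threshold is 3 weeks = 21 days, the lower edge of that window. On timing a replacing ETT Visit is a reasonable substitute. The gap is in content only.

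**Step 3: does another scheduled coagulation test follow the last dose?** After baseline and before Safety Follow-up, coagulation is scheduled only at nominal Days 15 and 29, in both parts. Day 43 has none, and neither does Day 57 in Part 2. Samples are taken before dosing. So for a last dose on day d and the earliest replacing ETT Visit at d + 21, a post-stop test exists only if some v in {15, 29} satisfies d < v ≤ d + 21.

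- Part 1, early stop, d = 1 to 28. For d = 1 to 14, v = 15 qualifies (the limiting case is d = 1, where 15 ≤ 22). For d = 15 to 28, v = 29 qualifies (the limiting case is d = 15, where 29 ≤ 36). Days without a test: 0 of 28.
- Part 2, early stop, d = 1 to 56, because TEZ/IVA counts as study drug (Section 10) and runs to Day 57. For d = 1 to 28 the result is as in Part 1. For d = 29 to 56 nothing qualifies. Days without a test: 56 − 29 + 1 = 28 of 56.

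A later ETT Visit changes neither result. These are counts of calendar days, not probabilities.

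**Step 4: if the nominal visits are not attended after stopping.** A Part 1 subject who stops before Day 15 and attends neither Day 15 nor Day 29 has only the screening and Day 1 predose coagulation results. One who stops after the Day 15 Visit and misses Day 29 has Day 15 and nothing after stopping. Whether these visits continue is unclear. Section 8.1.6 names only the ETT and Safety Follow-up Visits. Section 9.5 says in general terms that subjects withdrawn from treatment go on being followed, and footnote a of the tables provides for visits at which a discontinued subject receives no drug.

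**The case against.** **The route is an exception.** The ETT Visit is to be scheduled as soon as possible after the decision to stop. Normally it comes early and a full Safety Follow-up follows, with coagulation and a complete examination. This stands and limits the size. It does not close the route, because the ETT Visit is timed from the decision to terminate while replacement is counted from the last dose. A long interruption before that decision (Section 10.4 provides for interruption, investigation and possible resumption) can separate the two by weeks.

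**The analytic consequence is modest.** Safety analysis is descriptive. The SAP's laboratory threshold table (Table 11-10) has no coagulation parameter, so coagulation enters only the by-visit summaries and the out-of-range listing. Examination findings are only listed and are not among the named safety endpoints. Unscheduled tests may be done when clinically appropriate (Section 11.7.2). All of this stands, although a discretionary test is no substitute for a scheduled one.

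**The Part 2 gap concerns the washout.** By then the last VX-440 or placebo dose has been taken on Day 29, with a coagulation sample just before it, and completers have no coagulation test at Day 43 or Day 57 either. Completers who re-enter Study 661-110 have no Safety Follow-up at all (Section 8.1.5). That is correct. For the others, however, Safety Follow-up is the only scheduled coagulation test after both VX-440 and TEZ/IVA have stopped, and the replacement removes it.

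**The passages do not contradict each other.** Section 8.1.6 and the tables can be carried out as written. This also stands: the point is an omission, not a contradiction.

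**Conclusion.** The gap is real and small. A subject whose ETT Visit replaces Safety Follow-up loses the coagulation test and complete examination scheduled there. In Part 2, for a last dose on Day 29 to Day 56, the schedule itself then leaves no coagulation test after the last dose. Elsewhere that outcome also requires missed Day 15 or Day 29 visits. Primary efficacy is untouched, and redacted parts of the study could not be checked. The enumeration uses nominal visit days and ignores visit windows.

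Three stronger readings are tempting but not supported:

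- A reader might infer that anyone stopping before Day 15 on this route has no post-baseline coagulation value. That holds only if the later nominal visits are also missed, and Section 9.5 and footnote a suggest that follow-up may continue.
- A reader might size the problem by applying a dropout rate to the 42 + 24 = 66 subjects in Parts 1 and 2. The documents give no such rate. The product would count all early stoppers, most of whom should have an ordinary Safety Follow-up.
- A reader might infer that adverse event collection ends at the replacing ETT Visit. Under Section 13.1.1.3 it ends at the earlier of that visit or 28 days after the last dose. Either end point lies between 21 and 28 days, inside the normal follow-up window, so no defect is shown there.

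**What to change.** Amend Section 8.1.6 and footnote c so that an ETT Visit replacing Safety Follow-up collects the Safety Follow-up assessments, namely coagulation and a complete examination. Mark this condition in the ETT column of Protocol Tables 3-1 to 3-3 and of SAP Tables 11-1 to 11-3. In the same edit, state whether the nominal Day 15 and Day 29 visits continue after treatment is stopped.

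One SAP line is worth adding. Appendix B assigns Safety Follow-up by nominal visit, so the SAP should say whether a replacing ETT Visit is reported as Safety Follow-up. Otherwise the new result may be listed without appearing in that visit's summary.

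The cost is one more tube at a draw already scheduled for chemistry, hematology and PK, and a fuller examination at an existing visit. No visit is added.
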